8.1.2. Analysis of secondary endpoints

8.1.2.1. Analysis of secondary endpoint listed in 2.3.1.: *Estimate the cumulative proportion of HBsAg loss over time during and after treatment*

Cumulative proportion of HBsAg loss over time will be calculated using the product limit (Kaplan-Meier) method and presented with point-wise 95% confidence interval.

8.1.2.2. Analyses of other secondary endpoints

For all of the secondary endpoints listed in sections 2.3.1. – 2.3.4, we will provide frequencies and percentages with corresponding 95% confidence intervals. Time to such events may also be of interest (e.g. cumulative HBeAg loss). For time-to event analysis, Kaplan-Meier curves will be used to plot the cumulative proportion of events over time.

The second group of endpoints is continuous variables such as changes in ALT, HBV DNA levels from baseline at designated treatment or follow-up time points. Descriptive statistics, including measures of central tendency (e.g. means, medians) and estimates of spread (e.g., standard deviations, quartiles) will be used to characterize such changes. .

8.2. Missing data

Primary analyses will be performed using all enrolled participants (intention-to-treat analysis). Participants who do not have primary endpoint data due to drop-out or other reasons at the end of follow-up will be considered as treatment failures. Since this is a pilot study with a small sample size, formal procedures for handling missing data such as inverse-weighting and multiple imputation will not have enough power, nevertheless, we will apply the following methods to assess the sensitivity of our primary analysis results to different missing data assumptions:

1. Single LOCF Imputation: In this case the primary endpoint analysis will be repeated by replacing missing endpoint data at follow-up using data from prior visits.
2. Inverse-probability-weighting: This analysis will be carried out in two stages. In the first stage, for each subject we will estimate the probability of having complete data at week 96 based on the data collected at prior visits using logistic regression. In the second stage, the primary endpoint analyses will be repeated by weighting each subject with complete data by the inverse of the corresponding estimated probability from the first stage.
3. Multiple Imputations: The missing values at week 96 will be imputed by Markov-Chain Monte-Carlo algorithm, based on the data collected prior to week 96. Five such imputations will be used and the results of the primary endpoints analyses will be repeated on each of these imputed datasets and averaged.

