6.4. On-treatment assessments

After starting treatment, visits will occur at weeks 8, 12, 16, 20, 24, 30, 36, 42, and 48. Each visit will include assessment of compliance, adverse events reporting, vital signs, weight, symptoms evaluation, record of concomitant medications, and blood testing as detailed in Schedule of Events (Appendix I). Participants will be dispensed study medications.

1. At the Week 8 visit, peginterferon alfa-2a will be provided to subjects with instructions on its use, including education on self-injection, if appropriate. Subjects will have a limited clinical evaluation as well as blood and urine tests.

2. Pregnancy test will be done in women with reproductive potential at each visit until the end of treatment.
3. Depression assessment will occur at weeks 8, 12, 24, 36 and 48.
4. QOL assessments will occur at day 0, weeks 8 and 48. Health behaviors will be included at day 0 and week 48.
5. Fatigue questionnaire will occur at day 0.
6. CBC (with differential), hepatic panel (ALT, AST, total bilirubin), renal panel (Cr, CrCl) and HBV DNA quantitation at each visit.
7. TSH at week 12, 24, 36 and 48.
8. Albumin, alkaline phosphatase, glucose and total protein will be obtained at week 48
9. HBeAg at weeks 8, 12, 24, 36 and 48.
10. HBsAg at week 48.
11. Blood samples for serum/plasma at each visit.
12. HBsAg and HBeAg quantification at each visit.
13. Anti-HBs/HBe will be done at day 0 and week 48. Also at the next visit if HBsAg/HBeAg becomes negative.

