6.6. Post-treatment assessments

1. Visits will occur at weeks 52, 60, 72, and 96 .
2. Depression assessment will occur at weeks 60 and 96.
3. QOL and health behaviors assessments will occur at week 96.
4. Fatigue questionnaire will be obtained at week 96.
5. CBC (without differential), hepatic panel (ALT, AST, total bilirubin), renal panel (Cr, CrCl), and HBV DNA quantitation at each visit.
6. TSH at week 60.
7. Albumin, alkaline phosphatase, total protein, glucose, INR/PT, and urinalysis at week 96.
8. HBeAg at weeks 60, 72, and 96.
9. HBsAg at weeks 72 and 96.
10. HBsAg and HBeAg quantification every visit.
11. Blood samples for serum/plasma at each visit.
12. Anti-HBs/HBe will be done at week 96. Also at the next visit if HBsAg/HBeAg becomes negative.

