8.1.1. Analysis of primary endpoints

The primary endpoints include safety, measured by the rate of adverse and Serious Adverse Events, and efficacy, defined as loss of HBeAg and HBV DNA $\leq 1,000$ IU/mL at the end of follow-up (week 96). That is, only participants achieving HBeAg loss and having HBV DNA ≤ 1000 IU/mL at the end of follow-up will be considered as achieving the primary efficacy endpoint.

Safety

Summaries of adverse events (number of adverse events, number and percentage of participants with at least one adverse event, and for each adverse event, rate per person-years) will be provided. Events will be summarized based on the date of onset for the event. A treatment emergent adverse event will be defined as an adverse event that begins on or after the date of first dose of study drug.

Summaries of the following are planned:

- all adverse events recorded between screening and first dose of study medication,
- all treatment emergent adverse events,
- all emergent and related adverse events,
- all treatment emergent renal adverse events,
- all treatment emergent and related renal adverse events
- combined Grade 2, 3 and 4 treatment emergent adverse events,
- combined Grade 2, 3 and 4 related treatment and emergent adverse events,
- combined Grade 3 and 4 treatment emergent adverse events,
- combined Grade 3 and 4 related treatment and emergent adverse events,
- all adverse events that caused permanent discontinuation of study drug,
- all adverse events that caused temporary interruption of study drug,
- all serious adverse events, and
- all serious and related adverse events.

We will provide 95% confidence intervals for the rate of adverse and serious adverse events.

Efficacy

The percentage of participants achieving the primary efficacy endpoint will be summarized with the point estimate and 95% confidence interval.

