8.3. Sample size

This pilot study will enroll 40 participants into treatment. This sample size is considered to be achievable. We have calculated precision estimates based on various rates of primary endpoint of efficacy [loss of HBeAg and HBV DNA $\leq 1,000$ IU/mL at the end of follow-up (week 96)]. For example, if the expected proportion achieving primary efficacy endpoint is 25%, then we would be able to estimate it with 95% Clopper-Pearson confidence to ensure that the expected width of the interval does not exceed 29% (or equivalently, the estimated 95% confidence limits will be within $\pm 15\%$ of the estimate). Below are some further precision estimates:

Table: Precision (Width) Estimates for 95% Confidence Intervals under Different Primary Endpoint Proportions

Expected proportion with primary efficacy endpoint	95% lower	95% upper	Width
0.15	0.057	0.298	0.24
0.20	0.091	0.356	0.27
0.25	0.127	0.412	0.29

0.30	0.166	0.465	0.30
------	-------	-------	------

9. Data and safety monitoring board

Data and safety will be monitored by the National Institute of Diabetes and Digestive and Kidney Diseases (NIDDK) in conjunction with an NIDDK-appointed Data and Safety Monitoring Board (DSMB). This board serves in a consultative capacity to inform the NIDDK decisions regarding conduct of the study. The description of DSMB activities is included in the DSMB Charter.

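### The MCMC imputation in the third missing-data sensitivity analysis does not suit a yes/no composite in 40 participants, and the direction of its bias depends on choices the plan leaves open

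*Combined protocol and SAP*

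**What the plan says.** The primary efficacy endpoint is binary. Under section 8.1.1, "only participants achieving HBeAg loss and having HBV DNA" at or below 1,000 IU/mL at week 96 count as responders. Section 8.3 sets the size: "This pilot study will enroll 40 participants into treatment".

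Section 8.2 counts participants without week-96 data as failures in the primary analysis and adds three sensitivity analyses: LOCF, inverse-probability weighting and multiple imputation. On the last it says: "The missing values at week 96 will be imputed by Markov-Chain Monte-Carlo algorithm, based on the data collected prior to week 96". It continues: "Five such imputations will be used and the results of the primary endpoints analyses will be repeated on each of these imputed datasets and averaged".

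The earlier data are extensive. In section 6.4, "visits will occur at weeks 8, 12, 16, 20, 24, 30, 36, 42, and 48"; in section 6.6, "Visits will occur at weeks 52, 60, 72, and 96". With day 0 that makes 14 time points, 13 of them before week 96. Section 6.4 requires "HBV DNA quantitation at each visit", with ALT in the same list, and "HBsAg and HBeAg quantification at each visit"; section 6.6 and Appendix I continue these off treatment.

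Item 3 does not state the distribution, whether the composite or its components are imputed, which earlier variables enter, or how a draw becomes a yes or a no.

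**The concern.** An MCMC algorithm is a way of drawing values and does not fix a model. In its common form for imputation it draws from a joint normal distribution. HBeAg status is binary. Week-96 HBV DNA is plausibly two-humped, because entry requires more than 10^7 IU/mL (section 4.1) and off treatment a participant may stay suppressed or relapse to high levels. A single normal curve fits neither variable.

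The conditioning set is the second difficulty. Read broadly, the data before week 96 hold more variables than 40 participants can support, so the analyst would have to choose variables after seeing the data.

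Item 3 is one of only three checks on the missing-as-failure rule. If its answer depends on unstated modelling choices, it says little about robustness in either direction.

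**Working it through.** **Step 1. The plan's own figure.** Section 8.3 gives 95% Clopper-Pearson widths of 0.24, 0.27, 0.29 and 0.30 for expected proportions 0.15, 0.20, 0.25 and 0.30. Exact limits with x = 6, 8, 10 and 12 of 40 give 0.241, 0.266, 0.285 and 0.300, so the table reproduces. The width at 25%, about 29 points, is the yardstick below. The plan gives no figure for the imputation itself.

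**Step 2. Size of a joint-normal model.** With k variables there are k means and k(k+1)/2 variances and covariances. Over 14 time points, week 96 included:

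| Variables at all visits | k | Parameters |
|---|---|---|
| HBV DNA | 14 | 119 |
| + HBeAg quantification | 28 | 434 |
| + ALT | 42 | 945 |
| + HBsAg quantification | 56 | 1,652 |
| Composite + 3 predictors, for comparison | 4 | 14 |

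A parameter count above 40 is not the test: 14 HBV DNA values give 119 parameters but 14 × 40 = 560 data cells and a full-rank matrix. The limit is rank. A covariance matrix from 40 participants has rank at most 40 − 1 = 39, so k = 42 and k = 56 are singular. At k = 28 the model fits but is fragile. The last variable is regressed on 27 others plus an intercept (28 coefficients). With 20% missing, 32 − 28 = 4 residual degrees of freedom remain. With 30% missing, 28 − 28 = 0 remain, and in simulation none of the attempts could be fitted.

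**Step 3. Components imputed, then cut (closed form, no predictors).** Assumptions, not in the documents: responders' log10 HBV DNA is N(2, 0.6), non-responders' N(7.5, 1.0). The 25% response is the worked example in section 8.3.

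- Mean = 0.25 × 2 + 0.75 × 7.5 = 6.125.
- Variance = 0.25 × 0.36 + 0.75 × 1.0 + 0.25 × 0.75 × 5.5² = 6.51, so SD = 2.55.
- Normal model: P(log10 HBV DNA ≤ 3) = Φ((3 − 6.125)/2.55) = 0.110.
- True mixture: 0.25 × Φ((3 − 2)/0.6) = 0.238, with a negligible contribution from non-responders.
- Ratio = 0.110/0.238 = 0.46.

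**Step 4. Composite imputed as normal, rounded at 0.5 (closed form, no predictors).** The imputed rate is 1 − Φ((0.5 − p)/√(p(1−p))).

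| True p | Imputed | Ratio |
|---|---|---|
| 0.15 | 0.164 | 1.09 |
| 0.20 | 0.227 | 1.13 |
| 0.25 | 0.282 | 1.13 |
| 0.30 | 0.331 | 1.10 |

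**Step 5. Simulation with predictors.** With 40 participants, 25% response, and week-72 and baseline predictors, the imputed rate divided by the true rate among the missing was about 0.5 to 0.7 for components imputed and then cut. It was about 1.1 to 1.25 for the composite imputed and rounded. Across other assumed trajectories, predictor sets and 15% to 30% response, the first route ranged from about 0.2 to 0.8. The second ran from 0.93 (unrounded) to about 1.9 (rounded, all HBV DNA and HBeAg data, 10% to 20% missing).

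**Step 6. Effect on the overall estimate.** Shift = (missing/40) × 25% × (ratio − 1), in percentage points. The documents give no dropout rate, so the missing counts are assumed, with data missing at random.

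| Missing | Ratio 0.5 to 0.7 | Ratio 1.1 to 1.25 | Missing = failure gives |
|---|---|---|---|
| 4 | −1.25 to −0.75 | +0.25 to +0.6 | 22.5% |
| 8 | −2.5 to −1.5 | +0.5 to +1.25 | 20.0% |
| 12 | −3.75 to −2.25 | +0.75 to +1.9 | 17.5% |

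Even at ratio 0.5, the imputed estimates are 23.75%, 22.5% and 21.25%, halfway between missing-as-failure and the assumed 25%.

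**The case against.** The text names an algorithm; neither a normal distribution nor the use of every earlier variable is stated. A sensible analyst could run MCMC with a short variable list and a suitable model. This stands, and it is why the point is conditional on the joint-normal form.

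A reader might infer that the method halves the imputed response rate as a general property. The documents do not support that. It takes the choice to impute components and cut them, plus an assumed two-humped distribution; imputing the composite leaves the rate about right or too high at 15% to 30% response. The wording about missing values and imputed datasets makes the component route a natural reading, but it does not settle the matter.

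A reader might also infer that the analysis would agree with the missing-as-failure result by construction. Step 6 shows otherwise: the estimate lies above that result, and the gap widens with missingness.

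The plan itself concedes that formal missing-data methods lack power at this size, and LOCF and weighting stand beside item 3. That limits the consequence. But low power is a different matter from a model that fits the endpoint badly or cannot be estimated.

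Finally, the replacement carries its own risk. About 0.25 × 40 = 10 responders are expected, and late measures of the endpoint's components may separate the outcome perfectly. That risk is real, hence the penalised fit below.

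**Conclusion.** The point holds in a limited form. If item 3 is run as a joint-normal MCMC model, it suits the binary composite poorly, and whether it understates or overstates response among the missing depends on choices the plan does not make. At 25% response the overall estimate moves down by about 1 to 4 points, or up by at most about 2, with 4 to 12 missing. Both are small beside an interval about 29 points wide, and the primary analysis is untouched. These sizes rest on assumed HBV DNA distributions, assumed missing counts and missingness at random.

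The rank result needs no distributional assumption: three or more markers at all visits cannot be supported by 40 participants in such a model. Smaller all-visit sets become unstable as missingness grows. This is a cheap improvement to a sensitivity analysis.

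**What to change.** Replace the MCMC model in section 8.2, item 3 by one of two options, chosen in advance:

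- logistic imputation of the week-96 composite; or
- logistic imputation of HBeAg status together with predictive mean matching for log10 HBV DNA, with the composite derived afterwards.

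Name three predictors: last off-treatment HBeAg status, last off-treatment log10 HBV DNA and baseline log10 HBV DNA. Specify a penalised logistic fit in case of separation, and say how participants with no off-treatment measurement are handled.

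In simulation at 40 participants and 25% response, penalised logistic or predictive-mean-matching imputation with three predictors stayed within about 2 points of the true rate.

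The cost is one or two sentences of SAP wording and standard software. The downside is that fewer of the collected variables are used.

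### Five imputations leave avoidable seed noise, a standard deviation of about 1 to 1.8 points if 4 to 10 of 40 are missing, in the multiple-imputation sensitivity analysis

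*Combined protocol and SAP*

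**What the plan says.** The primary efficacy endpoint is yes/no. Under section 8.1.1, only participants with both HBeAg loss and HBV DNA at or below 1,000 IU/mL at week 96 "will be considered as achieving the primary efficacy endpoint". Section 8.3 sets the size: "This pilot study will enroll 40 participants into treatment".

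Section 8.2 makes the primary analysis one in which participants without week-96 data "due to drop-out or other reasons" count as failures. It then adds three analyses to test how far the result depends on the missing-data assumption: last observation carried forward, inverse-probability weighting and multiple imputation. On the third it says: "The missing values at week 96 will be imputed by Markov-Chain Monte-Carlo algorithm, based on the data collected prior to week 96". It continues "Five such imputations will be used", and the endpoint analyses "will be repeated on each of these imputed datasets and averaged".

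The section gives no random seed, no list of variables for the imputation model and no limit on Monte Carlo error. No dropout rate is stated anywhere in the documents.

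**The concern.** In a 40-person response rate, one participant is worth 1/40 = 2.5 percentage points. In each imputed data set, a missing participant is filled in as a responder or a non-responder by a random draw. Averaging only five such data sets leaves part of that randomness in the reported rate, so the same data analysed with another seed give another figure.

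This matters because of what the analysis is for. Its reader compares the imputed rate with the rate that counts missing as failure and asks how large the gap is. That gap is only a few points, so noise of a point or more is a sizeable part of it. A second analyst without the seed would not reproduce the figure. The issue is separate from how the five results are combined, since a correctly pooled estimate from five imputations depends on the seed just as much.

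**Working it through.** **The plan's own figure.** Section 8.3 uses a "95% Clopper-Pearson confidence" interval. For 10 responders of 40, the 2.5% quantile of Beta(10, 31) is 0.127 and the 97.5% quantile of Beta(11, 30) is 0.412. The width is 0.285, printed as 0.29, so the figure reproduces. N = 40 and a 25% response rate serve as the base case.

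**Inputs.** From the documents: N = 40, m = 5 imputations, 25% expected response (the table in section 8.3 runs from 15% to 30%). Assumed: k = 4 to 10 participants missing at week 96, and no predictive information from earlier visits.

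**Formula.** In each imputation, the response probability for the missing participants is drawn from Beta(a, b), with a = 0.25(40 − k) + 0.5 and b = 0.75(40 − k) + 0.5. The number of imputed responders Y is then binomial out of k. With q = a/(a + b) and a + b = 41 − k:

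- Var(Y) = k·q·(1 − q)·41/(42 − k)
- between-imputation variance of the rate, B = Var(Y)/40²
- seed-to-seed SD of the averaged rate = √(B/m)
- expected shift from missing-equals-failure = k·q/40

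**Example, k = 8.** q = 8.5/33 = 0.2576. Var(Y) = 8 × 0.2576 × 0.7424 × 41/34 = 1.845. B = 1.845/1600 = 0.001153. With m = 5, √(0.001153/5) = 0.0152, or 1.5 points. The expected shift is 8 × 0.2576/40 = 5.2 points.

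| Missing (k) | Missing = failure rate | Expected shift (points) | SD, m = 5 | SD, m = 50 | SD, m = 100 | SD/shift, m = 5 |
|---|---|---|---|---|---|---|
| 4 | 22.5% | 2.6 | 1.01 | 0.32 | 0.23 | 40% |
| 6 | 21.25% | 3.9 | 1.28 | 0.40 | 0.29 | 33% |
| 8 | 20.0% | 5.2 | 1.52 | 0.48 | 0.34 | 29% |
| 10 | 18.75% | 6.5 | 1.75 | 0.55 | 0.39 | 27% |

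(At k = 6 and k = 10, 25% of those observed is not a whole number of people; the rows are interpolations.) Simulation with 40,000 seeds per cell gives the same SDs at m = 5.

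**Two seeds compared, m = 5.** The median absolute difference is 1.0, 1.0, 1.5 and 1.5 points for k = 4, 6, 8 and 10. As a check, the normal approximation is 0.6745 × √2 × SD = 0.954 × SD, or 1.0 at k = 4 and 1.4 at k = 8. Differences of 3 points or more occur in about 5%, 13%, 20% and 27% of seed pairs.

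**Effect on the reported shift.** The central 95% of seeds give:

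- 4 missing: 1.0 to 4.5 points with m = 5; 2.1 to 3.0 with m = 100.
- 8 missing: 2.5 to 8.5 points with m = 5 (a rate of 22.5% to 28.5%, against 20% with missing as failure); 4.5 to 5.8 with m = 100.

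With m = 5, the reported shift is 1 point or less in about 9% of seeds with 4 missing and 0.2% with 8.

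**Varying the assumptions, m = 5.** Over response rates of 15% to 30%, the SD is 0.85 to 1.07 points with 4 missing and 1.28 to 1.60 with 8. With only 2 missing at 25% it is 0.70. If earlier visits predict well (illustration: a quarter of the missing have a response probability of 0.8 and the rest 0.067, held fixed), the variance of Y is k × (0.25 × 0.8 × 0.2 + 0.75 × 0.067 × 0.933) = 0.087k. The SD is then √(0.087 × 4/8000) = 0.7 points with 4 missing and √(0.087 × 8/8000) = 0.9 with 8.

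**The case against.** Only a sensitivity analysis is touched. The primary result uses no random numbers, the trial is a single-arm pilot with no hypothesis test, and its planned interval is about 29 points wide. The plan itself concedes that formal missing-data methods will be weak in so small a sample. Five imputations is a stated choice that contradicts nothing else in the documents, and a recorded seed alone would make the figure reproducible. Section 6.6 also schedules HBeAg at weeks 60 and 72 and HBV DNA at every follow-up visit, so a sensible imputation model should do better than the no-information case.

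Most of this stands and limits the point. Two parts do not remove it. The 29-point interval is the wrong yardstick, because it measures sampling uncertainty that both analyses share; the comparison of interest is between two treatments of the same 40 people, and that gap is a few points. A fixed seed also makes the number repeatable without making it more accurate. The concession about power concerns sample size, whereas Monte Carlo noise can be removed without another participant.

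A reader might infer that the response rate routinely moves by several points with the seed. It does not: typical differences are 1 to 1.5 points, and moves of 3 points or more remain a minority even with 10 missing. A reader might also infer that the noise could conceal or reverse the shift. An imputed rate cannot fall below the rate that counts every missing participant as a failure, so the direction is fixed. With 8 missing, the whole central 95% range lies above the primary result. Near-coincidence becomes common only with about 2 missing, where the shift itself is only about 1.3 points.

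**Conclusion.** The point holds as a small, free improvement. If 4 to 10 of 40 are missing, with 25% response among those observed and uninformative earlier visits, five imputations give a seed-to-seed SD of about 1.0 to 1.8 points. That is roughly 30% to 40% of the shift the analysis is meant to measure with 4 to 8 missing, and slightly less with 10. It blurs how large the sensitivity to missing data is, but seldom whether there is any.

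The number missing is an assumption, not a figure from the plan. With fewer missing or informative earlier visits the noise is smaller, and with nobody missing it vanishes. The documents do not support reading this as a threat to the primary result or to the trial's conclusions.

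**What to change.** In section 8.2, item 3, replace five imputations by at least 50, for example 100, and state the random seed and the software in advance. With 4 to 10 missing under the same assumptions, 50 imputations bring the SD down to about 0.3 to 0.55 points and 100 to about 0.2 to 0.4. The higher number makes the estimate precise; the seed makes it reproducible.

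The cost is one number and one added line in the plan, plus seconds of computing. No visit, clinical procedure or other analysis changes.

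### Section 8.2 averages the multiple-imputation results without a variance-pooling rule, so read literally its 95% interval does not widen as week-96 data go missing (minor)

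*Combined protocol and SAP*

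**What the plan says.** Section 8.1.1 (Efficacy) defines the output of the primary efficacy analysis: "The percentage of participants achieving the primary efficacy endpoint will be summarized with the point estimate and 95% confidence interval". It does not name the type of interval. Clopper-Pearson appears only in the precision calculation of section 8.3.

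Section 8.2 counts participants without week-96 endpoint data as failures in the primary analysis. It then lists three sensitivity analyses: last observation carried forward, inverse-probability weighting and multiple imputation. For the third, "The missing values at week 96 will be imputed by Markov-Chain Monte-Carlo algorithm, based on the data collected prior to week 96". The number of imputations is fixed ("Five such imputations will be used"), and the combining step is that "the results of the primary endpoints analyses will be repeated on each of these imputed datasets and averaged".

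Neither section 8 nor any other part of the document mentions Rubin's rules, a between-imputation variance, or another way to combine variances or confidence limits.

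**The concern.** Read together, sections 8.1.1 and 8.2 make the averaged object a proportion with its 95% interval. Each completed-data interval treats the imputed outcomes as if they had been observed. Averaging five such intervals keeps the within-imputation variance and drops the component that reflects not knowing the missing outcomes.

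The trial has no comparator and its sample size is justified by interval width alone, so the interval carries much of the efficacy message. The inverse-probability-weighted analysis uses only participants with complete data, so its interval, if properly computed, widens as data are lost. An averaged imputation interval would not. The imputation result could then look more precise than the weighted one purely because of how it was combined.

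**Working it through.** **Inputs from the plan.** n = 40 (section 8.3: "This pilot study will enroll 40 participants into treatment"); M = 5 imputations (section 8.2); response proportion p = 0.25 as the worked example, with a table from 0.15 to 0.30 (section 8.3).

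**Assumptions.** The plan states no missing rate, so k = 2, 4, 8 and 12 of 40 (5%, 10%, 20%, 30%) are used. Outcomes are missing completely at random and earlier visits carry no information about the missing outcome. The second assumption makes the results an upper range.

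**Step 1: the plan's own figures.** Exact Clopper-Pearson limits for 6, 8, 10 and 12 responders out of 40 are 0.057–0.298, 0.091–0.356, 0.127–0.412 and 0.166–0.465. The widths are 0.241, 0.266, 0.285 and 0.300. The section 8.3 table reproduces in full.

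**Step 2: the omitted variance.** With r = 40 − k observed:

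- Within-imputation variance: W = p(1 − p)/40
- Between-imputation variance: B = (k/40)² · p(1 − p)/r + k · p(1 − p)/1600, which simplifies to B = W · k/r
- Rubin's total variance: T = W + (1 + 1/M)B, so T/W = 1 + 1.2 · k/r, which does not depend on p

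Example at p = 0.25 and k = 4: W = 0.1875/40 = 0.0046875 and B = 0.0046875 × 4/36 = 0.000521. Then T = 0.0046875 + 1.2 × 0.000521 = 0.0053125, and √T = 0.0729 against √W = 0.0685.

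| Missing | T/W | SE, averaged | SE, pooled | SE ratio | Wald width, averaged | Rubin width (t) |
|---|---|---|---|---|---|---|
| 5% (2) | 1.063 | 0.0685 | 0.0706 | 1.031 | 0.268 | 0.287 |
| 10% (4) | 1.133 | 0.0685 | 0.0729 | 1.065 | 0.268 | 0.298 |
| 20% (8) | 1.300 | 0.0685 | 0.0781 | 1.140 | 0.268 | 0.325 |
| 30% (12) | 1.514 | 0.0685 | 0.0843 | 1.231 | 0.268 | 0.361 |

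The t quantile uses Barnard-Rubin degrees of freedom.

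**Step 3: coverage of nominal 95% intervals.** Simulation at p = 0.25 with 100,000 replicates per setting and proper imputation under a Beta(0.5, 0.5) prior:

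| Missing | Averaged Wald | Averaged Clopper-Pearson | Mean width of averaged Clopper-Pearson | Rubin, normal scale with t |
|---|---|---|---|---|
| 0% | 0.945 | 0.972 | 0.281 | 0.945 |
| 5% | 0.924 | 0.960 | 0.281 | 0.935 |
| 10% | 0.912 | 0.955 | 0.280 | 0.936 |
| 20% | 0.897 | 0.941 | 0.279 | 0.937 |
| 30% | 0.869 | 0.919 | 0.278 | 0.936 |

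The averaged Clopper-Pearson width stays near 0.28 throughout. Its built-in conservatism absorbs the missing variance up to about 10% missing, but not at 20% or more.

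**Step 4: which pooled interval to use.** The plain normal-scale Rubin interval stays at 0.935 to 0.937, below nominal and no better than averaged Clopper-Pearson until missingness exceeds 20%. A Clopper-Pearson interval computed at the effective sample size p(1 − p)/T covered 0.964 to 0.975 and widened with missingness. At p = 0.25 that effective size is 40 divided by T/W: about 37.6, 35.3, 30.8 and 26.4 at the four missing rates.

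**The case against.** The strongest objection is that section 8.2 never says that confidence limits or standard errors are averaged. Averaging is the correct rule for the point estimate, and the word may be shorthand for standard pooling. That stands as far as it goes: the documents neither confirm nor exclude it. A reader might infer that the sponsor has definitely committed to an invalid interval, and the text does not support that. It does leave an analyst who follows it literally with an interval that omits B, and nothing elsewhere supplies the missing rule.

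Second, the stated aim of these analyses is to compare the primary result under different missing-data assumptions. That is largely a comparison of estimates, and averaging gives the right one. This also stands and limits the consequence.

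Third, a reader might infer from the Wald figures that coverage generally drops to around 0.90. The plan never names a Wald interval. With Clopper-Pearson, the only type it names, the shortfall appears only from about 20% missing.

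Fourth, the size is an upper range. Section 6.6 schedules HBV DNA at every post-treatment visit and HBeAg at weeks 60 and 72, and the imputation uses data from before week 96. If an earlier marker is assumed to agree with the outcome 90% of the time, the SE ratio at p = 0.25 falls to 1.03, 1.07 and 1.12 at 10%, 20% and 30% missing. Averaged Clopper-Pearson then covers 0.961, 0.955 and 0.949, so little shortfall remains.

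Finally, a reader might infer that five imputations are themselves an error. They are not. At 30% missing, the SE ratio with M = 20 would be √(1 + 1.05 × 12/28) = 1.204 against 1.231 with M = 5, a change of about 2%. Likewise, imputing HBeAg status and HBV DNA separately is compatible with the present text, so asking for it would be a refinement.

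**Conclusion.** The point holds in a limited form. Section 8.2 gives a combining rule that is right for the estimate and incomplete for the interval. Followed literally, it produces an interval that does not respond to the amount of missing data.

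The pooled SE is 1.03 to 1.23 times the averaged SE, conditional on an assumed 5% to 30% missing and on uninformative earlier visits. How far coverage suffers depends on an interval type that sections 8.1.1 and 8.2 leave open: clearly with Wald, and only at about 20% missing or more with Clopper-Pearson.

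The documents do not support extending this to the trial's main efficacy result. The primary estimate and its interval rest on counting missing as failure and do not use the imputations. This is one of three sensitivity analyses in a 40-participant descriptive pilot. Severity is minor.

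**What to change.** In section 8.2, replace the instruction to average with a sentence such as: *Point estimates will be averaged across imputations and the variance pooled by Rubin's rules, T = W + (1 + 1/M)B, with the 95% confidence interval formed by a method suited to a small-sample proportion (for example Clopper-Pearson at the effective sample size p(1 − p)/T, or pooling on the logit scale).*

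The last clause matters. Specifying Rubin's rules with a plain normal-scale interval would give coverage of about 0.935 at p = 0.25, and about 0.925 to 0.93 at p = 0.15. Raising M and imputing the two endpoint components before deriving the composite are optional.

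The cost is one sentence, routine programming and a somewhat wider sensitivity interval. No change to data collection, sample size or the primary analysis is needed.
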